#### **5.2.2.2 Product Characteristics**

The drug substance is formulated in the surfactant Labrasol. The drug product is provided as 40 mg soft gelatin capsules in 124-count bottles with induction-sealed, child-resistant caps.

#### **5.2.2.3 Directions for Administration Enzalutamide**

Study participants will self-administer the total daily dose (160 mg) of enzalutamide as a single dose, once daily. Enzalutamide can be taken with or without food. Enzalutamide may be taken at any time during the day, but should be taken at the same time each day. A missed dose should be taken as soon it is remembered. If twelve or more hours have lapsed since their regularly scheduled time, patients should not take the missed dose; rather the patient should

CONFIDENTIAL

This document is confidential. Do not disclose or use except as authorized.

Version 13.0 Protocol Version Date: 1/09/2015

resume dosing at the next scheduled dose. Patients should not double up or take more than 1 dose of enzalutamide per day. Vomited doses should not be made up. Enzalutamide should not be crushed.

#### **5.2.2.4 Storage and Labeling**

Enzalutamide should be stored in a secure location with limited access at 77°F (25°C), with excursions permitted to 59°F to 86°F (15°C to 30°C). Bottles will be labeled with the study protocol number, medication or bottle number, contents, directions for use, storage directions, clinical trial statement, and Medivation Inc. as supplier. Patients will be instructed to store bottles containing enzalutamide capsules at room temperature

### **5.2.3 External Beam Radiation**

#### **5.2.3.1 Dose Specifications: 3D Conformal Radiotherapy (3DCRT) or IMRT**

Dose will be normalized such that exactly 98% of the PTV (planned target volume) receives the prescription dose and will be scored as per protocol. The maximum allowable dose within the PTV is 107% of the prescribed dose to a volume that is at least 0.03 cc. The minimum allowable dose within the PTV is >95% of the prescribed dose to a volume that is at least 0.03 cc.

EBRT shall receive prescription doses to the PTV 75.6- 79.2 Gy delivered in 1.8 Gy fractions. All attempts should be made to deliver the PTV dose with the above heterogeneity constraints with adherence to the critical structure parameters listed below:

Normal organ Limit *	No more than 15% volume receives dose that exceeds	No more than 25% volume receives dose that exceeds	No more than 35% volume receives dose that exceeds	No more than 50% volume receives dose that exceeds
Bladder Constraint	80 Gy	75 Gy	70 Gy	65 Gy
Rectum Constraint	75 Gy	70 Gy	66 Gy	60 Gy

#### **5.2.3.2 Technical Factors**

RT will be delivered with megavoltage equipment at energies  $\geq$  6 MV.

#### **5.2.3.3 EBRT Localization, Simulation, and Immobilization**

Simulation will be CT-based in all cases. The use of urethral contrast at the time of simulation is recommended but not required. The degree of bladder fullness should be made to duplicate that which is anticipated for daily treatment, i.e., if the patient is instructed to maintain a full bladder for treatment, he should be simulated as such (CT images should be acquired at a slice thickness of  $\leq$  3 mm from the top of the iliac crests superiorly to the perineum inferiorly. Target volumes and normal critical structures will be defined in the slices in which they are

CONFIDENTIAL

This document is confidential. Do not disclose or use except as authorized.

Version 13.0 Protocol Version Date: 1/09/2015

visualized. The 3DCRT cases must utilize “beam’s eye view” representations to define final beam aperture.

#### **5.2.3.4 Fiducial Placement:**

Fiducial markers placed within the prostate are required for this protocol. This procedure is routinely performed to permit pre-treatment imaging and position corrections to improve the precision of the external beam delivery (Image Guided Radiation Therapy). The placement of the three gold markers is performed by a Urologist. The fiducials are placed under transrectal ultrasound guidance. The fiducials are placed in the prostate so they do not overlap in the anterior and lateral x-ray projection.

Patients will be asked to participate in a procedure for correlative studies. This is not mandatory for participation. Two routine transrectal ultrasound guided biopsies will be taken in the location of previously identified disease on the diagnostic core biopsy report. These tissue samples will be stored for correlative tissue analysis.

#### **5.2.3.5 Treatment Planning/Target Volumes**

The definition of volumes will be in accordance with the ICRU Report #50: Prescribing, Recording, and Reporting Photon Beam Therapy. The Gross Tumor Volume (GTV) is defined by the physician as all known disease as defined by the planning CT, urethrogram, and clinical information. If a urethrogram is used, the GTV will encompass a volume inferiorly 5 mm superior to the tip of the dye and no less than the entire prostate. Prostate dimensions should be defined as visualized on CT scan.

The Clinical Target Volume (CTV) is the GTV plus areas considered to contain microscopic disease, delineated by the treating physician, and is defined as follows:

CTV is the GTV (prostate) plus areas at risk for microscopic disease extension plus the proximal bilateral seminal vesicles. Only the proximal 1.0 cm of seminal vesicle tissue adjacent to the prostate shall be included in the clinical target volume. This 1.0 cm of seminal vesicles refers to both radial (in plane) and superior (out of plane) extent. If both prostate and seminal vesicle are visualized in the same CT slice, this seminal vesicle tissue will contribute to the 1.0 cm of tissue. The Planning Target Volume (PTV) will provide a margin around the CTV to compensate for the variability of treatment set up and internal organ motion. A range of 5-10 mm around the CTV is required to define each respective PTV. Superior and inferior margins (capping) should be 5-8 mm depending on the thickness and spacing of the planning CT scan. Careful consideration should be made when defining the 5-8 mm margin in 3 dimensions. The ICRU Reference Points are to be located in the central part of the PTV and, secondly, on or near the central axis of the beams. Typically these points should be located on the beam axes or at the intersection of the beam axes.

Normal Critical Structures to be defined on the treatment planning CT scan will include the following: bladder, rectum (from its origin at the rectosigmoid flexure superiorly or the bottom of the SI joints, whichever is more inferior to the inferior-most extent of the ischial tuberosities), bilateral femora (to the level of ischial tuberosity), penile bulb and skin. Any

CONFIDENTIAL

This document is confidential. Do not disclose or use except as authorized.

small bowel within the primary beam aperture should be defined as well. All structures will be contoured in their entirety as solid organs.

Superior and inferior margins (capping) should be 5-10 mm depending on the thickness and spacing of the planning CT scan.

Careful consideration should be made when defining the 5-10 mm margin in 3 Dimensions. The PTV forms the entire target as described. No extension of fields to specifically treat regional lymph nodes is permitted. 3D conformal beams will be shaped to include the entire PTV and minimize dose to surrounding critical structures as described. Intensity modulated radiotherapy (IMRT) using inverse planning is permitted with constraints placed to adhere to critical structure dose limitations as defined above.

#### **5.2.3.6 Critical Structures**

Every effort should be made to deliver prescription doses to the PTV as specified while adhering to these constraints, it is recognized that certain anatomical factors may prevent this.

For purposes of compliance, up to a 5% absolute increase in the volume of critical structure receiving greater than the specified dose will be considered "variation acceptable," e.g. up to 20% of the rectum may receive a dose of > 75.6 Gy without a protocol deviation. Any increase in critical structure volume greater than 5% receiving more than the specified dose will be considered a "deviation unacceptable". The prescription dose should be the maximum deliverable up to 79.2 Gy while respecting the critical normal structure constraints. Of note, the penile bulb constraint is to be regarded as a guideline, and adherence to this should not, in any way, result in a reduction of the prescription dose or compromised dose coverage of the target volume.

#### **5.2.3.7 Treatment Verification**

First day port films or portal images of each field along with orthogonal isocenter verification films (or images) must be obtained. If modifications are made in field shaping or design, a port film of each modified field along with orthogonal isocenter verification films (or images) is required on the first day's treatment of that field. Thereafter, weekly verification films or images of orthogonal isocenter views (anterior to posterior and lateral projection) are required. The intensity profiles of each beam must be independently verified and compared to the planned field intensity. Portal films are not required for IMRT but orthogonal verification films are required. Daily on-line target localization (kV or MV imaging with fiducials) should be performed.

#### **5.2.3.8 Quality Assurance Documentation**

Requirements:

The institution will archive treatment prescription and verification images for later review by the study chair if requested. At least one port film or pretreatment alignment film per field along with the digital reconstructed radiographs (DRRs) from the treatment planning program or, alternatively, a simulation verification radiograph shall be acquired and kept for evaluation if requested except where geometrically impractical

CONFIDENTIAL

This document is confidential. Do not disclose or use except as authorized.

### 5.2.3.9 Compliance Criteria

The minimum allowable dose within the PTV is >95% of the prescribed dose to a volume that is at least 0.03cc. Cases in which this small volume of at least 0.03cc receives a minimum dose that is <95% but >93% or a maximum dose that is >107% and <110% of the prescribed dose will be scored as a variation acceptable. Cases in which such a small volume receives less than 93% or >110% of the prescribed dose will be scored as a deviation and unacceptable. Acceptable dose heterogeneity will be as follows: **This maximum dose volume of the PTV must not be shared by a normal critical structure.** The maximum point dose to normal critical structures outside the PTV should not exceed the prescription dose.

The treating physician must carefully consider the tolerance dose/volume to each critical normal structure and unspecified tissue.

## 5.3 General Concomitant Medication and Supportive Care Guidelines

### 5.3.1 Prior and Concomitant Therapy

**5.3.1.1** Medications taken within 14 days prior to the first dose of study drug will be documented on the appropriate case report form as a prior medication. Medications taken after the first dose of study medication and until 30 days following the last dose of any study drug (enzalutamide) will be documented on the appropriate case report form as concomitant medication. All concomitant medication(s) must be reported on the appropriate case report form. Prior and concomitant medications include all vitamins, herbal remedies, over the counter, and prescription medications. If an intermittent or as needed use of any medication during the study is due to an adverse event, then the adverse event must also be recorded on the adverse event case report form.

**5.3.1.2** The following medications are prohibited within 4 weeks of first study drug administration and throughout time on study, unless otherwise indicated below:

Androgens (e.g., testosterone, dihydroepiandrosterone), estrogens, or progestational agents Ketoconazole, diethylstilbestrol, PC-SPES, and other preparations such as saw palmetto thought to have endocrine effects on prostate cancer:

- Radiopharmaceuticals such as strontium (89Sr) or samarium (153Sm), radium 223 ○ Aldactone, Spironol (spironolactone), eplerenone;
- Herbal medications, such as Prostasol and PC-SPES, St. Jon's Wort; ○ Cancer Vaccine therapy;
- Non-cytotoxic, non-investigational anti-tumor treatment;
- Use of an investigational agent, unless prior approval by the PI, [name], for a shorter washout period, provided the patient has adequately recovered from any ongoing adverse events.
- Any alternative remedy that may affect hormonal status.

CONFIDENTIAL

This document is confidential. Do not disclose or use except as authorized.

Version 13.0 Protocol Version Date: 1/09/2015

- Caution is advised for patients taking drugs metabolized through either CYP3A4 or CYP2C8 pathways. Please see Appendix F.

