In mice, rats, and dogs, orally administered enzalutamide had a half-life (t1/2) of approximately 0.25 to 3 days. The t1/2 did not appear to be affected by the dose size; however, bioavailability appeared to decrease with increasing dose size. Plasma protein binding of enzalutamide in human plasma ranged from 97% to 98% and was similar in mice, rats, rabbits, and dogs.

Co-administration of a strong CYP2C8 inhibitor (gemfibrozil) increased the composite area under the plasma concentration-time curve (AUC) of enzalutamide plus N-desmethyl enzalutamide in healthy volunteers. Co-administration of enzalutamide with strong CYP2C8 inhibitors should be avoided (see APPENDIX F).

The effects of CYP2C8 inducers on the pharmacokinetics of enzalutamide have not been evaluated in vivo. Co-administration of enzalutamide with strong CYP2C8 inducers (e.g., rifampin) may alter the plasma exposure of enzalutamide and should be avoided (see APPENDIX F).

The effects of CYP3A4 inducers on the pharmacokinetics of enzalutamide have not been evaluated in vivo. Co-administration of enzalutamide with strong CYP3A4 inducers (e.g., carbamazepine, phenobarbital, phenytoin, rifabutin, rifampin, rifapentine) may decrease the plasma exposure of enzalutamide and should be avoided. (see APPENDIX F) Moderate CYP3A4 inducers (e.g., bosentan, efavirenz, etravirine, modafinil, nafcillin) and St. John's Wort may also reduce the plasma exposure of enzalutamide and should be avoided.

Enzalutamide is a strong CYP3A4 inducer and a moderate CYP2C9 and CYP2C19 inducer in humans. At steady state, enzalutamide reduced the plasma exposure to midazolam (CYP3A4 substrate), warfarin (CYP2C9 substrate), and omeprazole (CYP2C19 substrate).

Concomitant use of enzalutamide with narrow therapeutic index drugs that are metabolized by CYP3A4 (e.g., alfentanil, cyclosporine, dihydroergotamine, ergotamine, fentanyl, pimozide, quinidine, sirolimus and tacrolimus), CYP2C9 (e.g., phenytoin, warfarin), pentobarbital, ketoconazole, sertaraline, digitoxin, haloperidol, ketamine, doxycycline, isoniazid, ciprofloxacin and CYP2C19 (e.g., S-mephenytoin) should be avoided if possible, as enzalutamide may

CONFIDENTIAL

This document is confidential. Do not disclose or use except as authorized.

Version 13.0 Protocol Version Date: 1/09/2015

decrease their exposure. If co-administration with warfarin cannot be avoided, conduct additional INR monitoring

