**Appendix F:**

Drugs to avoid because of interaction with CYP2C8 or CYP3A4 metabolic pathways

Gemfibrizil, carbamazepine, phenobarbital, pentobarbital, phenytoin, rifabutin, rifampin, rifapentine, nafcillin, modafinil, etavirenz, efavirenz, bosentan, cyclosporin, ergotamine, quinidine, sirolimus, tacrolimus, alfentanil, pimozide, St. John's Wort, ketoconazole, sertraline, digitoxin, haloperidol, ketamine, doxycycline, isoniazid, etravirine, dihydroergotamine and fentanyl.

Drugs to be used with caution

Warfarin (will likely require a change in warfarin dosing), omeprazole, midazolam, ciprofloxacin.

CONFIDENTIAL

This document is confidential. Do not disclose or use except as authorized

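### The caution rule in section 5.3.1.2 names CYP3A4 and CYP2C8, but section 2.1 gives CYP3A4, CYP2C9 and CYP2C19 as the pathways enzalutamide induces; the remaining gap is small and concerns drugs not listed by name

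*Combined protocol and SAP*

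**What the plan says.** Four places in the protocol bear on drug interactions.

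- **Section 5.3.1.2**, the on-study medication rule, ends with a class statement: "Caution is advised for patients taking drugs metabolized through either CYP3A4 or CYP2C8 pathways". Its next sentence sends the reader to Appendix F.
- **Section 2.1**, the pharmacology text, says "Enzalutamide is a strong CYP3A4 inducer and a moderate CYP2C9 and CYP2C19 inducer in humans". It reports that at steady state "enzalutamide reduced the plasma exposure to midazolam (CYP3A4 substrate), warfarin (CYP2C9 substrate), and omeprazole (CYP2C19 substrate"). It asks that narrow-therapeutic-index substrates of these enzymes be avoided where possible; for the CYP2C19 group it reads "CYP2C19 (e.g., S-mephenytoin) should be avoided if possible, as enzalutamide may" lower their exposure. CYP2C8 appears in the other direction only: "Co-administration of enzalutamide with strong CYP2C8 inhibitors should be avoided (see APPENDIX F"), and "Co-administration of enzalutamide with strong CYP2C8 inducers (e.g., rifampin) may alter the plasma exposure of enzalutamide and should be avoided".
- **Appendix F** has two lists. The first is headed "Drugs to avoid because of interaction with CYP2C8 or CYP3A4 metabolic pathways". The second, the caution list, has a heading that states no pathway and reads "Warfarin (will likely require a change in warfarin dosing), omeprazole, midazolam, ciprofloxacin".
- **Exclusion 3.2.17** excludes any man who needs a drug on either Appendix F list.

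**The concern.** The rule in 5.3.1.2 is worded in terms of how the other drug is metabolised, so it is a rule about substrates. Section 2.1 supports a different set of substrate pathways. The rule appears to merge two kinds of interaction: drugs that alter enzalutamide (where CYP2C8 belongs) and drugs that enzalutamide alters (where CYP2C9 and CYP2C19 belong).

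This matters for drugs that Appendix F does not name. Section 2.1 gives its CYP2C9 and CYP2C19 drugs as examples of a class, so a list of names cannot fully stand in for a correct class statement. New medication during the study is foreseeable from the protocol itself: antibiotics around fiducial placement (section 2.4), alpha blockers and NSAIDs (6.2.1.1), loperamide (6.2.1.2), prophylactic medication (6.2.2.3) and antiemetics (6.3). Nothing is claimed here about which pathway any of these uses. The point is only that sites will meet unlisted drugs and may turn to the class rule. At stake is a consistent safety instruction for up to 71 men over 24 weeks of dosing.

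**Working it through.** No error rate, power or event count enters this point. The check sets the texts side by side and counts.

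**Step 1. Pathways.**

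| Pathway | Section 2.1: enzalutamide lowers substrate exposure | Section 2.1: other drugs alter enzalutamide | 5.3.1.2: caution for substrates |
|---|---|---|---|
| CYP3A4 | Yes (strong inducer) | Yes (inducers) | Yes |
| CYP2C9 | Yes (moderate inducer) | Not mentioned | No |
| CYP2C19 | Yes (moderate inducer) | Not mentioned | No |
| CYP2C8 | Not mentioned | Yes (inhibitors and inducers) | Yes |

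The supported substrate set is {3A4, 2C9, 2C19}; the rule gives {3A4, 2C8}. One pathway matches, two of three are missing, and one has no stated basis.

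**Step 2. Named drugs.** Each drug named in the interaction text of section 2.1 was looked up in Appendix F, allowing for spelling variants. Each drug is counted once, in the first row where it appears.

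| Group in section 2.1 | New names | In Appendix F |
|---|---|---|
| CYP3A4 narrow-index examples | 9 | 9 (avoid) |
| CYP2C9 examples: phenytoin, warfarin | 2 | 2 (avoid; caution) |
| Names in the same sentence with no clear pathway, including ciprofloxacin | 9 | 9 (8 avoid, ciprofloxacin caution) |
| CYP2C19 example: S-mephenytoin | 1 | 0 |
| Drugs with measured reduction: midazolam, omeprazole (warfarin already counted) | 2 | 2 (caution) |
| CYP2C8 modulators: gemfibrozil, rifampin | 2 | 2 (avoid) |
| CYP3A4 inducers, including St. John's Wort (12 named, phenytoin and rifampin already counted) | 10 | 10 (avoid) |

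Names: 9 + 2 + 9 + 1 + 2 + 2 + 10 = 35. Listed: 9 + 2 + 9 + 0 + 2 + 2 + 10 = 34.

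Of the four drugs that section 2.1 gives as CYP2C9 or CYP2C19 substrates (phenytoin, warfarin, omeprazole, S-mephenytoin), three are in Appendix F. Phenytoin is also named in section 2.1 as a CYP3A4 inducer, so its place on the avoid list does not by itself show that CYP2C9 was considered.

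**Step 3. Reach of the eligibility rule.** Exclusion 3.2.17 works through the Appendix F lists. It therefore covers the 34 listed drugs at entry and does not reach an unlisted CYP2C9 or CYP2C19 drug.

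**Step 4. Drugs handled differently in different places.** Warfarin and ciprofloxacin fall in the section 2.1 sentence on drugs to be avoided where possible. Appendix F puts both on the caution list. Exclusion 3.2.17 bars men who need either.

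**The case against.** The strongest reply is that the bullet in 5.3.1.2 does not stand alone. It points to Appendix F, where coverage by name is nearly complete, and 3.2.17 applies both lists at entry, more strictly than section 2.1 asks. Section 2.1 is in the same protocol and carries its own instructions, including extra INR monitoring with warfarin, and concomitant medication is reviewed at the 28-day visits. This stands, and it reduces the gap to unlisted drugs plus S-mephenytoin. It does not remove the mismatch, because both the class rule and 3.2.17 pass over an unlisted CYP2C9 or CYP2C19 drug.

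A second reply concerns the Appendix F heading. It sits over the avoid list only and speaks of interaction, which suits the CYP2C8 and CYP3A4 modulators beneath it. Warfarin and omeprazole are in the other list. This also stands: the heading is at most incomplete. A reader might infer that Appendix F as a whole rests on the wrong enzymes; its contents do not support that.

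On warfarin and ciprofloxacin, one can read 3.2.17 as governing entry and the caution list as governing later use, and avoidance where possible is not far from caution. That reading is reasonable, but the protocol does not state it.

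**Conclusion.** This is a real but minor internal inconsistency. Relative to section 2.1, the class rule in 5.3.1.2 omits two of three induced pathways and names CYP2C8 as a substrate pathway without stated support. The uncovered group is narrow-therapeutic-index CYP2C9 or CYP2C19 drugs not named in Appendix F, whether needed at entry or started on study. The differing treatment of warfarin and ciprofloxacin is a related conflict.

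A reader might infer that sites are told to check the wrong pathways. The documents do not support that: CYP3A4, the only enzyme that section 2.1 calls strongly induced, is named correctly. Nor do they support an estimate of harm, since medication use in this population is not given and no affected drug beyond S-mephenytoin can be identified from the text.

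The conclusion takes section 2.1 as the protocol's own statement of the pharmacology and assumes that at least some sites would apply the class rule to a drug they do not find in Appendix F.

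**What to change.** Reconcile sections 2.1, 3.2.17, 5.3.1.2 and Appendix F so that the class rule and both lists agree with the pharmacology text. In particular:

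- bring the pathways in the 5.3.1.2 bullet into line with section 2.1, and check whether the avoid-list heading in Appendix F is complete;
- resolve or explain the absence of S-mephenytoin from Appendix F;
- state how section 2.1, the caution list and 3.2.17 fit together for warfarin and ciprofloxacin, at entry and on study.

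The sponsor decides the content; no drug rule is proposed here. The cost is the wording of one bullet, a check of one appendix and its heading, and a cross-check of 3.2.17. No endpoint, sample size or analysis changes.
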